4.6.6 Treatment Beyond Disease Progression

As described in [Section 1.1.4](#), accumulating evidence indicated a minority of subjects treated with immunotherapy may derive clinical benefit despite initial evidence of progressive disease.⁴⁹

Subjects treated with nivolumab will be permitted to continue treatment beyond initial Investigator-assessed RECIST 1.1-defined progressive disease as long as they meet the following criteria:

- Investigator-assessed clinical benefit and do not have rapid disease progression
- Tolerance of study drug
- Stable performance status
- Treatment beyond progression will not delay an imminent intervention to prevent serious complications of disease progression (eg, CNS metastases)
- Subject provides written informed consent prior to receiving additional nivolumab treatment using an ICF describing any reasonably foreseeable risk or discomforts or other alternative treatment options

The assessment of clinical benefit should be balanced by clinical judgment as to whether the subject is clinical deteriorating and unlikely to receive any benefit from continued treatment with nivolumab.

All decisions to continue treatment beyond initial progression must be discussed with the BMS Medical Monitor and documented in the study records.

Subjects must sign a separate informed consent form to receive treatment beyond progression.

Subjects should discontinue study therapy upon evidence of further progression, defined as an additional $\geq 10\%$ increase in tumor burden volume from time of initial progression (including all target lesions and new measurable lesions).

Global deterioration of health status requiring discontinuation of treatment without objective evidence of disease progression at the time should be reported as symptomatic deterioration. Every effort should be made to document objective progression (ie, radiographic confirmation) even after discontinuation of treatment.

4.6.7 Treatment of Nivolumab-Related Infusion Reactions

Since nivolumab contains only human immunoglobulin protein sequences, it is unlikely to be immunogenic and induce infusion or hypersensitivity reactions. However, if such a reaction were to occur, it might manifest with fever, chills, rigors, headache, rash, pruritus, arthralgias, hypotension, hypertension, bronchospasm, or other allergic-like reactions. All Grade 3 or 4 infusion reactions should be reported within 24 hours to the study medical monitor and reported as an SAE if it meets the criteria. Infusion reactions should be graded according to NCI CTCAE (Version 4.0) guidelines.

Treatment recommendations are provided below and may be modified based on local treatment standards and guidelines, as appropriate:

For Grade 1 symptoms: (Mild reaction; infusion interruption not indicated; intervention not indicated).

Remain at bedside and monitor subject until recovery from symptoms. The following prophylactic premedications are recommended for future infusions: diphenhydramine 50 mg (or equivalent) and/or acetaminophen/paracetamol 325 to 1000 mg at least 30 minutes before additional nivolumab administrations.

For Grade 2 symptoms: (Moderate reaction requires therapy or infusion interruption but responds promptly to symptomatic treatment [eg, antihistamines, non-steroidal anti-inflammatory drugs, narcotics, corticosteroids, bronchodilators, IV fluids]; prophylactic medications indicated for ≤ 24 hours).

Stop the nivolumab infusion, begin an IV infusion of normal saline, and treat the subject with diphenhydramine 50 mg IV (or equivalent) and/or paracetamol 325 to 1000 mg (acetaminophen); remain at bedside and monitor subject until resolution of symptoms. Corticosteroid or

bronchodilator therapy may also be administered as appropriate. If the infusion is interrupted, then restart the infusion at 50% of the original infusion rate when symptoms resolve; if no further complications ensue after 30 minutes, the rate may be increased to 100% of the original infusion rate. Monitor subject closely. If symptoms recur, then no further nivolumab will be administered at that visit. Administer diphenhydramine 50 mg IV and remain at bedside and monitor the subject until resolution of symptoms. The amount of study drug infused must be recorded on the electronic case report form (eCRF). The following prophylactic premedications are recommended for future infusions: diphenhydramine 50 mg (or equivalent) and/or paracetamol 325 to 1000 mg (acetaminophen); these should be administered at least 30 minutes before additional nivolumab administrations. If necessary, corticosteroids (recommended dose: up to 25 mg of IV hydrocortisone or equivalent) may be used.

For Grade 3 or 4 symptoms: (Severe reaction, Grade 3: prolonged [ie, not rapidly responsive to symptomatic medication and/or brief interruption of infusion]; recurrence of symptoms following initial improvement; hospitalization indicated for other clinical sequelae [eg, renal impairment, pulmonary infiltrates]. Grade 4: life-threatening; pressor or ventilatory support indicated).

Immediately discontinue infusion of nivolumab. Begin an IV infusion of normal saline and treat the subject as follows: recommend bronchodilators, epinephrine 0.2 to 1 mg of a 1:1000 solution for subcutaneous administration or 0.1 to 0.25 mg of a 1:10,000 solution injected slowly for IV administration, and/or diphenhydramine 50 mg IV with methylprednisolone 100 mg IV (or equivalent), as needed. Subject should be monitored until the Investigator is comfortable that the symptoms will not recur. Nivolumab will be permanently discontinued.

Investigators should follow their institutional guidelines for the treatment of anaphylaxis. Remain at bedside and monitor subject until recovery of the symptoms. In case of late-occurring hypersensitivity symptoms (eg, appearance of a localized or generalized pruritus within 1 week after treatment), symptomatic treatment may be given (eg, oral antihistamine or corticosteroids).

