7.6.1.2 Select Adverse Events

Categories of “select AEs” have been created to group together the most common and impactful preferred terms (PTs) by organ category, providing a better estimate of the frequency of similar kinds of organ-related AEs instead of using PTs only. These select adverse events are further defined as follows:

- may differ from or be more severe than AEs caused by non-immunotherapies
- may require unique (non-standard) intervention such as immunosuppressants (or hormone replacement therapy)
- early recognition and management may mitigate severe toxicity

The preferred terms included in the ‘select AEs’ category are those that are expected to be most commonly used to describe pneumonitis, interstitial nephritis, diarrhea/colitis, hepatitis, rash, and endocrinopathies. Hypersensitivity/infusion reactions are also considered a select AE category to facilitate the pooling of the most relevant preferred terms for analyses of hypersensitivity/infusion reaction events and not because such events fit the criteria for select AEs.

Select AEs are based on the list provided by BMS every 6 months.

Unless otherwise specified, analysis will be performed by select AE category and ECOG PS group: Some analyses may also be repeated by subcategory of endocrine events.

- Overall summary of any select AEs overall and by worst CTC grade presented by Category or Subcategory/PT A presentation of by age category will also be provided. Overall summary of drug-related select AEs by worst CTC grade presented by Category or Subcategory / PT
- Overall summary of any serious select AEs by worst CTC grade presented by Category or Subcategory /PT
- Overall summary of drug-related serious select AEs by worst CTC grade presented by Category or Subcategory /PT. A presentation of by age category will also be provided.
- Overall summary of serious select Endocrine AEs by worst CTC grade presented by Category or Subcategory /PT
- Overall summary of drug-related serious select Endocrine AEs by worst CTC grade presented by Category or Subcategory /PT
- Overall summary of any select AEs leading to discontinuation overall and by worst CTC grade presented by Category or Subcategory /PT

- Overall summary of drug-related select AEs leading to discontinuation overall and by worst CTC grade presented by Category or Subcategory /PT

The analyses will be conducted using the 30-day safety window and repeated using the 100-day safety window.

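### Protocol 4.6.7 gives two different dosing consequences for an infusion reaction that resolves, is restarted and then recurs

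*Protocol*

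**What the plan says.** Protocol 4.6.7 sets a single grading standard ("Infusion reactions should be graded according to NCI CTCAE (Version 4.0) guidelines") and then gives recommendations grade by grade.

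- **Grade 2 paragraph.** The infusion is stopped and the subject treated. Then: "If the infusion is interrupted, then restart the infusion at 50% of the original infusion rate when symptoms resolve". If the reaction returns: "If symptoms recur, then no further nivolumab will be administered at that visit". The paragraph closes with premedication advice for later infusions, saying of the premedications that "these should be administered at least 30 minutes before additional nivolumab administrations".
- **Grade 3 or 4 paragraph.** The Grade 3 description has three parts: a prolonged reaction, "recurrence of symptoms following initial improvement", and hospitalization for other sequelae. The action ends: "Nivolumab will be permanently discontinued". No exception is given in the section.
- **Reporting.** Earlier in the same section: "All Grade 3 or 4 infusion reactions should be reported within 24 hours to the study medical monitor". No such duty is stated there for Grade 2.

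On the analysis side, SAP 7.6.1.2 states: "Hypersensitivity/infusion reactions are also considered a select AE category". It plans summaries of select events by worst CTC grade, and of those leading to discontinuation. Protocol 8.3.1 defines select adverse events by reference to Protocol 4.6.1. The seven groups listed there are pulmonary, gastrointestinal, endocrine, hepatic, renal, skin and neurological; infusion reactions are not among them.

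**The concern.** A subject who improves, is restarted and reacts again fits the Grade 2 instruction, which was written for exactly that situation. The same subject also fits the wording of the Grade 3 description. Under one paragraph later dosing stays open; under the other it is closed for good. Two sites, each following the protocol, could treat the same subject in opposite ways.

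Three things depend on the reading:

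1. whether the subject is exposed to the drug again;
2. whether the 24-hour report to the medical monitor is made;
3. possibly, which grade goes on the CRF, and so which side of the Grade 2/Grade 3 line the event falls on in the SAP's infusion-reaction tables.

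**Working it through.** The documents give no figure to reproduce, so the check is a comparison of texts for one fixed sequence: reaction, interruption, resolution, restart at reduced rate, recurrence.

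| Question | Grade 2 paragraph | Grade 3 or 4 paragraph |
|---|---|---|
| Does the sequence fit? | Yes; recurrence after restart is addressed explicitly | Yes; recurrence after improvement is one of the listed Grade 3 features |
| Further drug at this visit? | No | No |
| Drug at later visits? | Left open; the stop is limited to one visit and premedication for later infusions follows | No; discontinuation is permanent |
| 24-hour report to the medical monitor? | Not required by 4.6.7 | Required |

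The paragraphs agree on the current visit and part company on every later one.

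I then looked for text elsewhere that would settle which paragraph applies.

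- **Protocol 4.6.7, opening text.** It names CTCAE v4.0 as the grading standard but does not say that a recurrence under the Grade 2 paragraph is regraded, or that the Grade 3 paragraph then takes over. It also lets sites adapt the recommendations to local standards, which permits variation without resolving the conflict.
- **Protocol 4.6.2 and 4.6.4.** A Grade 2 non-skin drug-related event calls for dose delay, with resumption once it is back to Grade 1 or less, or to baseline. A site that keeps the event at Grade 2 therefore finds further support for dosing again.
- **Protocol 4.6.5.1.** Grade 3 infusion reactions are named among the exceptions to the rule for Grade 3 events lasting more than 7 days, but no action is stated for them there. The general item on substantial clinical risk leaves the decision to the investigator.
- **SAP 7.6.1.1 and 7.6.1.2.** Neither gives a grading rule for recurrence. The list of categories in 7.6.1.1 is cut short in the public text and cannot help.

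Nothing found settles it.

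**Path into the analysis.** If a recurrence is recorded as Grade 2 at one site and Grade 3 at another, the worst-grade rows for the SAP's hypersensitivity/infusion-reaction category change. If one site stops treatment and another does not, the rows for select events leading to discontinuation change. SAP 7.6 presents any grade, Grades 3-4 and Grade 5, so the first shift would cross a reported boundary.

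**The case against.** The best defence is that the Grade 2 text describes bedside action only. It never says that a recurrence remains Grade 2. A site could stop the infusion that day, grade the recurrence by the section's own Grade 3 description, and then follow the Grade 3 paragraph; stopping for one visit does not logically exclude stopping for good. It can be added that the Grade 2 restart requires symptoms to have resolved, whereas the Grade 3 wording speaks of improvement, so two different courses may be meant. The premedication advice may also have been intended only for subjects without a recurrence. Finally, these are recommendations open to local modification.

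Part of this stands. The difference in recorded grade is an inference, so sites *could* grade differently; it cannot be said that they will. The rest does not remove the conflict. Limiting the stop to one visit would be a strange way to introduce permanent discontinuation. Resolution is ordinarily a form of improvement, and no sentence separates the two. Freedom to adapt locally does not say which of two instructions is being adapted.

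A reader might also infer two stronger consequences that the documents do not support.

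- **That the primary endpoint moves with the reading.** Protocol 8.3.1 takes its definition from 4.6.1, which omits infusion reactions. The SAP adds the category for pooling and says in the same sentence that such events are not there because they meet the select-event criteria.
- **That the ambiguity is as large as the rates the trial was sized to detect.** Protocol 8.1 and SAP section 5 both say that the sample size is logistical. The rare-event rates in those sections illustrate precision for a single rare event. With no infusion-reaction or recurrence rate in either document, any count of affected subjects would be a guess.

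**Conclusion.** The contradiction is real and explicit as regards later dosing, and with it the 24-hour report. It is plausible, but not stated, as regards the recorded grade. Neither document says which paragraph governs.

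The effect on the analysis is narrow: the worst-grade and leading-to-discontinuation tables for the SAP's hypersensitivity/infusion-reaction category. Its size cannot be derived, and the case for correction does not depend on it. A safety instruction that gives two answers for one subject should be put right however rare the event.

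The conclusion rests on two readings: that recurrence after resolution falls within the Grade 3 wording, and that a stop limited to one visit implies that later dosing is possible. Both are the ordinary sense of the words. No view is taken here on which clinical rule should apply.

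**What to change.** The sponsor's clinical team should reconcile the two paragraphs of Protocol 4.6.7. The revised text should state, for a reaction that recurs after the infusion is restarted, which grade is recorded and which paragraph then governs further dosing and reporting. If the two paragraphs are meant for different courses, the text should say what separates them. The same rule should go into the CRF completion guideline so that the grade and the reason for discontinuation are recorded alike at all sites.

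The cost is one or two sentences in the protocol and a matching line in the guideline, with no added visits, procedures or subjects. The SAP tables can stay as planned.

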4.7 Blinding/Unblinding

Not applicable

4.8 Treatment Compliance

Treatment compliance will be monitored by drug accountability as well as by the subject's medical record and eCRF.

4.9 Destruction of Study Drug

For this study, study drugs (those supplied by BMS or sourced by the investigator) such as partially used study drug containers, vials and syringes may be destroyed on site.

Any unused study drugs can only be destroyed after being inspected and reconciled by the responsible Study Monitor unless study drug containers must be immediately destroyed as required for safety, or to meet local regulations (eg, cytotoxics or biologics).

On-site destruction is allowed provided the following minimal standards are met:

- On-site disposal practices must not expose humans to risks from the drug.
- On-site disposal practices and procedures are in agreement with applicable laws and regulations, including any special requirements for controlled or hazardous substances.
- Written procedures for on-site disposal are available and followed. The procedures must be filed with the site's SOPs and a copy provided to BMS upon request.
- Records are maintained that allow for traceability of each container, including the date disposed of, quantity disposed, and identification of the person disposing the containers. The method of disposal, ie, incinerator, licensed sanitary landfill, or licensed waste disposal vendor must be documented.
- Accountability and disposal records are complete, up-to-date, and available for the Monitor to review throughout the clinical trial period.

If conditions for destruction cannot be met the responsible Study Monitor will make arrangements for return of study drug.

4.10 Return of Study Drug

If study drug will not be destroyed upon completion or termination of the study, all unused and/or partially used study drug that was supplied by BMS must be returned to BMS. The return of study drug will be arranged by the responsible Study Monitor.

It is the investigator's responsibility to arrange for disposal of all empty containers, provided that procedures for proper disposal have been established according to applicable federal, state, local, and institutional guidelines and procedures, and provided that appropriate records of disposal are kept.

Arrangements for the return of study drug will be made by the responsible Study Monitor.

5 STUDY ASSESSMENTS AND PROCEDURES

5.1 Flow Chart/Time and Events Schedule

Table 5.1-1: Screening Procedure Outline (CA209171)

Procedure	Screening Visit ^a	Notes
Eligibility Assessments		
Informed Consent	X	
Inclusion/Exclusion Criteria	X	Assessed prior to first dose
Medical History	X	Medical history will include smoking history, comorbidities, particularly chronic pulmonary and chronic cardiovascular diseases following international established categories (eg, NYHA for cardiac insufficiency). Mutation status of EGFR and ALK will be collected and ROS, MET, KRAS, and BRAF will be collected, if available. Additional biopsies for mutation status, if not previously tested, are not required.
Safety Assessments		
HIV testing (in Germany only)	X	
Physical Examination	X	Includes height, weight, and ECOG PS. Focused physical exam may be performed at screening if clinically indicated.
ECOG Performance Status	X	Subgroup 1: PS 0-1 Subgroup 2: PS 2
Vital Signs and Oxygen Saturation	X	Temperature, BP, HR, RR, O2 saturation by pulse oximetry at rest (also monitor amount of supplement oxygen if applicable). Obtain vital signs at screening visit and within 72 hours of first dose.
Assessment of Signs and Symptoms	X	After obtaining Informed Consent, assess all signs and symptoms within 14 days of first dose, prior to study treatment initiation.
██████████	█	██████████
Serious Adverse Events Assessment	X	
Adverse Events Assessment	X	

Table 5.1-1: Screening Procedure Outline (CA209171)

Procedure	Screening Visit ^a	Notes
[REDACTED]	■	[REDACTED]
Pregnancy Test	X	Performed within 24 hours prior to first dose for WOCBP only (serum or urine as required by the standard of care at the site)
Additional Assessments		
[REDACTED]	■	[REDACTED]
Efficacy Assessment		
Screening/Baseline Tumor Assessment		Chest, abdomen, pelvis, brain, and all other known sites of disease within 28 days prior to first dose of study therapy. Subjects must have evaluable disease by CT or MRI per RECIST 1.1 criteria (radiographic tumor assessment performed within 28 days of first dose of study drug) or clinically apparent disease that the investigator can follow for response.

ALT = Alanine aminotransferase; AST = Aspartate aminotransferase; BP = blood pressure; BUN = blood urea nitrogen; CBC = complete blood count; HBsAg = hepatitis B surface antigen; HCV Ab = hepatitis C antibody; HR = heart rate; LDH = lactate dehydrogenase; O2 = oxygen; PS = Performance Status; RR = respiratory rate; TFT = Thyroid Function Test; TSH, thyroid stimulating hormone; WOCBP = women of child bearing potential.

^a Within 28 days before start of nivolumab

Table 5.1-2: CA209171 On-treatment Assessments

Procedure	Each Cycle (every 2 weeks)	Every 2 Cycles (every 4 weeks)	Every 3 Cycles (every 6 weeks)	Week 9	Week 52	Notes
Safety Assessments						
Physical Measurements (including Performance Status)	X					Collect weight and ECOG Performance Status within 72 hours prior to dosing. Focused physical examination may be performed if clinically indicated.
Vital Signs and Oxygen Saturation	X					Within 72 hours prior to dosing, tests includes temperature, BP, HR, RR, O2 saturation by pulse oximetry at rest (also monitor amount of supplemental oxygen if applicable) prior to dosing and at any time a subject has any new or worsening respiratory symptoms.
Serious Adverse Event Assessment	X					Assessed using NCI CTCAE v 4.0
Adverse Events Assessment	X					Assessed using NCI CTCAE v 4.0
[REDACTED]	[REDACTED]					
[REDACTED]	[REDACTED]		[REDACTED]			[REDACTED]
Pregnancy Test		X				Completed more frequently if required by local standards (serum or urine as required by standard of care at the site).

Table 5.1-2: CA209171 On-treatment Assessments

Procedure	Each Cycle (every 2 weeks)	Every 2 Cycles (every 4 weeks)	Every 3 Cycles (every 6 weeks)	Week 9	Week 52	Notes
Assessments						
Tumor Scans				X	X	Mandatory tumor assessments are to be done at Weeks 9 and 52 (±5 days) according to RECIST 1.1 criteria. Additional assessments should be performed according to local standards of care or at the investigator’s discretion and are recommended every 8-12 weeks. Assessments should include chest, abdomen, and all known or suspected sites of disease.
█		█	█			█
Survival	X					
Clinical Drug Supplies						
Administration of Study Drug	X					All subjects continue treatment every 2 weeks until disease progression, unacceptable toxicity, or withdrawal of informed consent. Treatment for all subjects can continue beyond initial investigator-assessed progression, if the subject has investigator-assessed clinical benefit and is tolerating the study drug. Record Study Drug Infusion start and stop times.

BP = blood pressure; CBC = complete blood count; HR = heart rate; █

█ NCI CTCAE = National Cancer Institute Common Terminology Criteria for AEs; O2 = oxygen; PS = Performance Status; RR = respiratory rate.

^a CBCs with differential includes white blood cell count, lymphocyte count, absolute neutrophil count, hemoglobin, hematocrit, and platelet count. Results to be obtained prior to dosing on infusion days.

[REDACTED]

Table 5.1-3: CA209171 Off-Treatment Follow Up Assessments				
Procedure	FU1 6 weeks (±2 weeks) after last dose	FU2 16 weeks (±2 weeks) after last dose	Further Follow-Up Every 3 months (±1 month) after FU2	Notes
				every 8-12 weeks. Assessments should include chest, abdomen, and all known or suspected sites of disease.
Survival Follow Up	X	X	X ^b	

^b In-person visit or telephone call

